#### **VERSION NUMBER/DATE:**

## **REVISION HISTORY:**

Revision #	Version Date	Summary of Changes	Consent Change?
V4	10.04.2022	Minor language corrections and further detail provided	Yes
V5	12.23.2022	Section 7.5 Specifics of pre vs post release fund distribution removed due to some participants returning to the community prior to accessing DOC account funds Section 5.1 and 5.4 updated to include EHR review as a source of information on SUD as it pertains to eligibility Section 13.1 updated to indicate that in the case of a participant's study phone being lost or stolen, a replacement phone will be hand delivered by the nurse case manager in the community	Yes

		Section 13.4 updated to indicate that we will collect any history of substance use from participant, not only in 3 months prior to	
		incarceration Section 15.1: participants will be considered lost to follow up after 5 unsuccessful attempts to contact, but will not be removed from the study. Their study phone line may be turned off at that point. A study member will attempt to contact them at 3 m post-release in order to complete the end-of-study assessment Section 27: Defined all documents used in study, differentiated research tools to be attached separately from case management process tools available upon request.	
V6	02.16.2023	Eligibility criteria updated to reflect current procedure for determining eligibility, which is based on participant report at time of screening and not on COMPAS or EMR data.  Updated recruitment process: sending recruitment letters to all releasees and determining eligibility based on answers to screener, wait list utilization for subset of eligible participants prior to enrollment  Updated procedures for making incentive funds available to participants  Procedure for phone termination were uniformized to "might be turned off" after a month of unsuccessful attempts to contact, as it may be decided to continue funding the phone line in order to attempt to collect the end-of-study assessment  Removed medical information form as it is no longer in use  Clarified that research baseline survey will be done EITHER by NCM or other study team member and can be done in person or over the phone  Clarified NCM interaction with participants after release (weekly) and after attended outpatient appointment (minimal), and study team member will call at 3m post-release to administer end-of-study survey and possibly exit interview section 15.3 Differentiated subsequent steps after withdrawal and subsequent steps after participant declines some aspect of study activities  Other forms edited:  Consent  ROI  Eligibility screener	Yes

		

Research Baseline Survey

NCM Intake Assessment

	
V7	03.24.2023	DOC Facility changed from Taycheedah Correctional Institution to Wisconsin Women's Correctional System (WWCS) ROI language clarified Name of 3 Month Survey uniformized Plan for collection of modified survey questions for early participants still incarcerated stated Intended mechanism to measure Appropriateness updated	No
V8	05.03.2023	Procedures to facilitate a participant retaining their study provided cell phone number after completion of research activities have been added Procedures for waitlist vs direct enrollment updated to facilitate workflow.	No

Page 3 of 37 Revised: February 16, 2023

# **Study Summary**

Study Title	Health systems innovations for supporting transitions of care for incarcerated people living with HIV, Hepatitis C, and substance use disorder
Brief Summary	This protocol describes the second, implementation phase of a 5-year NIH-funded research project designed to evaluate post-incarceration health care utilization and outcomes for underserved people living with HIV, HCV and substance use disorder. In the first study phase, conducted from 2020-21 (UW IRB ID# 2020-0749), we analyzed Wisconsin Medicaid data to characterize the baseline level of outpatient care utilization for adults during their first 6 months after release from prison, and conducted formative research necessary to adapt an existing transitional care intervention, called C-TraC, to support individuals leaving prison. The current project aims to enroll participants in a pilot implementation study to test the feasibility and acceptability of the adapted intervention in a criminal justice setting, which we have given the name "CJC-TraC."
Number of study	1
sites	
Study Design	Single Group Behavioral Intervention
Primary Objective	To evaluate the feasibility and acceptability of CJC-TraC when implemented in a state prison system.
Secondary	To gather preliminary evidence describing the effectiveness of CJC-
Objective(s)	TraC for improving the rate of outpatient care utilization
Research	Criminal Justice Coordinated Transitional Care (CJC-TraC) Program, a
Intervention(s)/	multi-session transitional case management intervention bridging the
Investigational	pre-release and post-release period.
Agent(s)	
Drugs/devices used	n/a
on study (including	
any IND/IDE #)	
Study Population	Individuals incarcerated in Wisconsin living with HIV, Hepatitis C, or history of substance misuse preparing for release
Sample Size	220
Study Duration for	Up to 6 months (3 months before release and 3 months after release
individual	from prison)
participants	, , , , , , , , , , , , , , , , , , ,
Study Specific	NCM-Nurse Case Manager
Abbreviations/	CJC-TraC- Criminal Justice Coordinated Transitional Care
Definitions	

Note: Include only elements relevant to this study.

Page 5 of 37

# 1.0 Background

# 1.1 Describe the relevant prior experience and gaps in current knowledge.

The goal of this project is to adapt an evidence-based case management intervention that was developed in acute care hospital settings to support health care for people preparing to be released from prison. The original hospital-based program, called the Coordinated Transitions of Care (C-TraC) project, is a transitional care model created to support adults with chronic conditions who are discharging from the hospital back to the community. C-TraC uses nurse case managers who follow the patient during their hospital stay and through the discharge process, continuing care after the patient returns to the community. The Nurse Case Manager participates in daily rounds with the inhospital health care team. After discharge, the Nurse Case Manager connects with the patient virtually to conduct medication reconciliation, review of upcoming appointments, review of 'red flags' (signs or symptoms of a potentially dangerous health event).

We have designed a mixed-methods approach based on the Replicating Effective Programs (REP) Implementation Theory Model to adapt C-TraC framework, processes, and goals to the context of correctional health care.

# 1.2 Describe any relevant preliminary data.

In the completed first phase of this project, we made a variety of discoveries.

In Aims 1 & 2 [*Please see IRB ID 2020-0749 & 2019-0058*] we examined individual-, area-, and system-level factors that may influence access to care following release from prison. The study cohort for Aim 1 included adults living with, or at risk of, SUD, HCV, or HIV who were enrolled in Medicaid at the time of their release from Wisconsin state prison. Preliminary results indicated that within 30-days of their release, approximately 34% of the study population has at least one outpatient visit. Women are more likely than men to have this visit as are White individuals compared to Black individuals. Receipt of prescription medication indicated for the following conditions during the 12-months before release from prison strongly increase the likelihood of an outpatient visit within 30-days: HIV, depression, diabetes, pain, Parkinson's disease, psychotic illness, osteoporosis/Paget's, and alcohol dependence. Aim 2 examined the impact of assistance with Medicaid enrollment pre-release on access to care among those with and without a history of SUD. For those with a history of SUD, we find significant increases in the likelihood of outpatient care for any cause and related to substance use disorders. However, the absolute rate of SUD-related care remains low.

AIM 3: Qualitative research done from 2019-2021 contributed directly to how the C-TraC intervention was modified to fit the present study's target population. Firstly, general challenges (e.g. access to transportation, access to cell phones) were identified by both the focus group participants as well as the interview participants. This information allowed us to consider the scope of the Nurse Case Manager's intervention and how these needs could be met while controlling the scale of the intervention to a feasible level.

Interviews conducted with formerly incarcerated adults also yielded valuable information concerning the importance of rapport and trust building with people who are incarcerated. Based on interviews with formerly incarcerated individuals, strategies have been added to the Nurse Case Manager protocol to individualize case management to prevent participants from feeling like the Nurse Case Manager is using a checklist or "just doing a job".

Interview participants were asked what they believed would be the most effective way to implement the intervention, including the number of visits with a Nurse Case Manager prior to release, how long before release meetings should be initiated, how long and how often meetings should occur following release, and the specific issues that formerly incarcerated person would likely need assistance with. Their responses were used to inform the final structure of the intervention.

Page 6 of 37 Revised: February 16, 2023

1.3 Provide the scientific or scholarly background for, rationale for, and significance of the research based on the existing literature and how will it add to existing knowledge.

Human Immunodeficiency Virus (HIV), Hepatitis C virus (HCV) infection, and substance use disorders (SUD) represent interdependent epidemics of enormous public health significance. In the past decade, HCV surpassed HIV/AIDS as the leading cause of infectious death among U.S. adults, while opioid overdose overtook motor vehicle accidents as the number one injury-related cause of death. Evidence-based strategies to effectively prevent and manage these conditions exist, yet recent outbreaks of HCV and HIV among people who inject opioid in socioeconomically disadvantaged communities in the U.S. illustrate the failure to deliver such services in the settings where they are most urgently needed. Criminal justice system involvement is highly prevalent among people who inject drugs, and incarcerated populations have a disproportionately high burden of HIV, HCV, and opioid use disorders. Further, their transitions back into the community are plagued by poor coordination, including poor access to treatment and a resulting high risk of death after release.

This project represents an innovative adaptation of a low-cost transitional care intervention [Aim 3 of the parent study IRB ID 2020-0749] to the context of criminal justice-related health systems that is feasible, effective, and sustainable.

# 2.0 Study Objectives and Endpoints

2.1 Describe the purpose, specific aims, or objectives. An objective is the purpose for performing the study in terms of the scientific question to be answered. Express each objective as a statement of purpose (e.g., to assess, to determine, to compare, to evaluate) and include the general purpose (e.g., effectiveness, safety) and/or specific purpose (e.g., effect of an intervention on health behavior, utility of an assessment method).

The main objective of this project is to adapt and evaluate the feasibility and acceptability of a low cost, evidence based transitional care program, called C-TraC, for increasing use of outpatient medical care for incarcerated people with HIV, HCV and/or opioid use disorder.

We have designed a mixed-methods approach based on the Replicating Effective Programs (REP) Implementation Theory Model to adapt C-TraC processes and goals to the context of correctional health care. Formative research conducted during the first phase of this study in 2020-2021 [UW IRB ID: 2020-0749 and WIDOC RRC Application ID: [name] 1912] identified they key processes necessary for successfully supporting patients with complex medical and behavioral health challenges as they navigate outpatient health services. Focus groups, interviews, and informal discussions with Wisconsin Department of Corrections (WIDOC) staff also informed the operational details for successful implementation of the pilot protocol at two WIDOC institutions which are described in this protocol. After completion of the pilot trial, we will have gained experience about successful implementation strategies as well as unanticipated challenges and will have collected preliminary data about the effectiveness of the CJC-TraC intervention for improving post-incarceration health outcomes that will be used for planning future studies designed to formally test the effectiveness and cost effectiveness of CJC-TraC.

# State the hypotheses to be tested.

The main hypothesis to be tested in this pilot study is that the CJC-TraC protocol developed in collaboration with WIDOC partners will be successfully implemented in a way that is deemed acceptable to WIDOC staff and incarcerated patients. We will consider implementation to be successful if (1) we enroll a substantial number of eligible participants (e.g. at least 50% of the targeted sample size of 220), and (2) Participants complete post-incarceration study activities with a reasonable rate of retention (e.g. fewer than 50% of participants being lost to follow-up after

release). We will assess acceptability by systematically querying study participants and WIDOC staff about their experience with CJC-TraC using validated questionnaires, as described below.

A secondary hypothesis is that individuals who participate in the CJC-TraC pilot will have a higher rate of using non-emergency, outpatient health services (e.g. primary care clinic appointment) after incarceration, in comparison to contemporaneous rates of health service utilization by individuals with comparable levels of comorbidities and demographic characteristics.

2.2 Define the primary and secondary study endpoints. A study endpoint is a specific measurement or observation to assess the effect of the study variable (study intervention). Study endpoints should be prioritized and should correspond to the study objectives and hypotheses being tested.

In this pilot study we will assess endpoints related to feasibility, acceptability, and effectiveness, as described above:

Primary Endpoints: Feasibility

- The number of participants who are enrolled and complete the baseline study assessment per month, at each of two institutions;
- The number of pre-release CJC-TraC intervention sessions completed with the nurse case manager for each participant, at each institution;
- The number of post-release telephone contacts between the CJC-TraC nurse case manager and study participants;
- The proportion of study participants who are retained in follow-up for three months and complete the end-of-study assessment.

Primary Endpoints: Acceptability

- The proportion of study participants who rated specific aspects of the intervention useful and encounter volumes appropriate, collected on 3 month survey.
- The subjective experience in the program regarding prison-to-community transition support and healthcare support, collected by participant interview.
- The proportion of DOC staff who rated the intervention acceptable, useful, or appropriate, collected by DOC staff survey.

The referred to questions assess attitudes regarding appropriateness and acceptability of the CJC-TraC intervention, and do not include questions about respondents themselves. Pilot intervention participants and WIDOC staff involved with the CJC-TraC pilot program at Wisconsin Women's Correctional System (WWCS) and Oakhill Correctional Institutions will be asked questions to capture perceptions about the intervention itself at the conclusion of the pilot intervention. WIDOC staff are not considered research subjects as a result of being asked these questions as they are not being asked to share data about themselves, but rather professionally assess the intervention. In addition to assessing the acceptability and appropriateness of CJC-TraC, pilot intervention participants provide additional identifiable and personal data throughout the lifespan of the study and are therefore considered research participants.

Secondary Endpoints: Effectiveness

- The number of non-emergency outpatient visits observed within 3-months following release.
- The number days until the first non-emergency outpatient visit following release.

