#### 12.1 Describe:

• The duration of an individual participant's participation in the study.

**Primary Objective (feasibility and acceptability):** We will engage with study participants who are within 3 months of release from prison and will follow them up to 3 months after release.

Interactions between the study team and participants will end upon completion of the 3 Month Survey and exit interview following a post-release outpatient visit or after 3 months of follow up. The final assessment may be delayed no-longer than 6 months after release if the participant is incarcerated, hospitalized or out of contact with the study team for other reasons. Data will continue to be collected from the Medicaid database for 1 year after release from prison.

**Secondary Objective (preliminary assessment of effectiveness):** This objective only involves secondary data analysis using administrative data. This objective does not require any in-person encounters with participants or site visits to either WIDOC facility in the study. We plan to use population-level data of all individuals >=18 years of age released from the Wisconsin Department of Corrections between 1/1/2020-12/31/2023.

• The duration anticipated to enroll all study participants.

Primary objective: We plan to have enrollment open for two years.

**Secondary Objective (preliminary assessment of effectiveness):** This objective only involves secondary data analysis using administrative data. This objective does not require any in-person encounters with participants or site visits to either WIDOC facility in the study. We plan to use population-level data of all individuals >=18 years of age released from the Wisconsin Department of Corrections between 1/1/2020-12/31/2023.

• The estimated date for the researchers to complete this study (complete primary analyses).

Primary and Secondary Objectives: Analysis is anticipated to be completed by June 2025.

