# 15.0 Withdrawal of Participants

15.1 Describe anticipated circumstances under which participants will be withdrawn from the research without their consent.

**Primary Objective (feasibility and acceptability):** Participants will be withdrawn if they're exhibiting ongoing aggressive, harassing, or threatening behavior. Participants will be evaluated individually by the Nurse Case Manager and research staff, and the subject may be removed from study if we feel it is in the best interest of the subject, staff, and other study participants.

Participants will also be removed from the study if they have an extension to their sentence and they are no longer within 3 months of release. They will be eligible to re-enroll in the study if their release date falls within 3 months while the study is ongoing.

Page 26 of 37 Revised: February 16, 2023

The Nurse Case Manager will attempt to reach the participant 4 times after release. On the 5th unsuccessful contact attempt, the participant will be considered lost to follow up and the nurse case manager will cease attempts to contact. The Nurse Case Manager will fill out the Post-Release Contact Log to keep track of these attempts. [See Contact Log] If the participant has a cell phone provided by the study, the cell phone's plan may be terminated at this point. A study team member will attempt to contact the participant through various means to complete the End-of-Study Assessment.

**Secondary Objective (preliminary assessment of effectiveness):** Not applicable. Preliminary assessments for effectiveness only involves secondary data analysis using administrative data. This objective does not require any in-person encounters with participants or site visits to either WIDOC facility in the study.

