# 15.3 Describe procedures that will be followed when participants withdraw from the research, including partial withdrawal from procedures with continued data collection.

**Primary Objective:** If participants wish to withdraw from the study, they can do so at any time by contacting the Nurse Case Manager or any of the study contacts listed in the consent form. If a participant indicates they wish to withdraw, they will not be asked to complete the 3 month survey or exit interview as detailed above. If a participant indicates that they do not wish to participate in any aspect of the intervention (i.e. phone calls with the case manager after release), they will be allowed to decline. They will be asked if they would agree to participate in the 3 month survey and potentially the exit interview. They will receive the same compensation as participants who completed all aspects of the study. Both the 3 month survey and the option for an exit interview are documented in the consent form.

Any meetings or appointments with health care providers or others that have already been scheduled will remain in place in the event of a participant's premature withdrawal from the study.

**Secondary Objective:** Not applicable. Preliminary assessments for effectiveness only involves secondary data analysis using administrative data. This objective does not require any in-person encounters with participants or site visits to either WIDOC facility in the study.

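### Does the lost-to-follow-up wording in success criterion (2) clash with the retention endpoint in Section 2.2?

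*Combined protocol and SAP*

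**What the plan says.** Three parts of the protocol bear on retention.

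- **Section 2.1, success criterion (2).** Success requires that "Participants complete post-incarceration study activities with a reasonable rate of retention (e.g. fewer than 50% of participants being lost to follow-up" after release. The figure is given as an example, as is the enrolment figure in criterion (1), at least half of the target of 220.
- **Section 2.2, feasibility endpoints.** The retention endpoint is "The proportion of study participants who are retained in follow-up for three months and complete the end-of-study assessment".
- **Section 15.1, withdrawal.** "On the 5th unsuccessful contact attempt, the participant will be considered lost to follow up", and the nurse then stops calling. The same paragraph continues: "A study team member will attempt to contact the participant through various means to complete the End-of-Study Assessment". The V5 entry in the revision history says the same of such people: "participants will be considered lost to follow up after 5 unsuccessful attempts to contact, but will not be removed from the study".

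Two further provisions affect who completes the survey. Section 15.3 says: "If a participant indicates they wish to withdraw, they will not be asked to complete the 3 month survey or exit interview". Section 12.1 allows the final assessment to be delayed "no-longer than 6 months after release if the participant is incarcerated, hospitalized or out of contact with the study team" for other reasons.

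**The concern.** Section 15.1 is the only place that says when a participant counts as lost to follow-up. If that definition is carried into criterion (2), the success threshold counts failed nurse contact, while the endpoint counts completed assessments. Someone the nurse cannot reach but whom another team member later surveys is lost under 15.1 and may still be a completer. Someone who withdraws after release is never asked for the survey, so is a non-completer, yet is not lost under 15.1.

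Retention is one of only two conditions for calling implementation successful. If the true figure lies near one half, the success statement and the primary endpoint could point in different directions, and the authors could choose the kinder count after seeing the data.

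**Working it through.** **Inputs.** From the documents: target 220 (Sections 2.1 and 3.0) and the 50% example (Section 2.1). The protocol gives no expected loss or survey-completion rate, so there is no plan figure to reproduce and every rate below is an assumption. For simplicity all 220 are taken as released.

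**Step 1: the threshold in counts.** Fewer than 50% of 220 lost means at most 109. More than half completing means at least 111. Since 220 − 109 = 111, the two rules coincide if lost and completed are exact complements.

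**Step 2: where they are not complements.**

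| Participant | Lost under 15.1? | Meets the 2.2 endpoint? |
|---|---|---|
| Not lost, surveyed | No | Yes |
| Nurse contact failed, never surveyed | Yes | No |
| Not lost, but withdrew, was removed or declined the survey | No | No |
| Nurse contact failed, later surveyed by other staff | Yes | Open: surveyed, but retained for three months? |

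The third row breaks the complement. The fourth does so only if such a person counts as retained in follow-up for three months. Section 2.2 asks for retention as well as the assessment, and staying in the study, as the V5 entry has it, is not plainly the same thing.

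**Step 3: size when a 15.1-lost person cannot meet the endpoint.** With n lost and completion c among the others, completers = c × (220 − n). The threshold is met but completion is half or less when n ≤ 109 and c × (220 − n) ≤ 110.

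- c = 70%: 220 − 110/0.7 = 62.9, so conflict at 63–109 lost.
- c = 80%: 220 − 110/0.8 = 82.5, so conflict at 83–109 lost.
- c = 90%: 220 − 110/0.9 = 97.8, so conflict at 98–109 lost.
- c = 100%: 220 − 110 = 110, so no conflict.

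At c = 80% and 100 lost (45.5%), completers are 0.8 × 120 = 96, or 43.6%. At 60 lost (27.3%), they are 0.8 × 160 = 128, or 58.2%, and the two rules agree.

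**Step 4: size when a later survey does count.** Completers = a × n + c × (220 − n), with a the completion rate among the lost.

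- a = 10%, c = 80%, 100 lost: 10 + 96 = 106, or 48.2% (exact 95% CI 41.4 to 55.0). The threshold is met and completion is below half. Break-even is (176 − 110)/0.7 = 94.3, so conflict at 95–109 lost.
- a = 20%, c = 80%: break-even is (176 − 110)/0.6 = 110, so no conflict at any n.
- a = 30%, c = 90%, 120 lost (54.5%): 36 + 90 = 126, or 57.3% (50.4 to 63.9). The threshold is missed and completion is above half. Break-even is (198 − 110)/0.6 = 146.7, so conflict at 110–146 lost.

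The last case exists only under this step's reading. With a = 0 and c = 90%, 120 lost gives 0.9 × 100 = 90 completers, or 40.9%, and both rules fail together.

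**Step 5: size on the natural reading.** If lost to follow-up in Section 2.1 means not meeting the 2.2 endpoint, completers = 220 − lost by definition. The rules then agree at every count, apart from the tie at exactly 110, where neither is met.

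**The case for a change.** The strongest case for a change is that the protocol defines the term once, in 15.1, and differently from the endpoint. Nothing in Section 20 repairs this: 20.1 restates the primary hypothesis with no threshold, and 20.6 has no rule for classifying non-completers. If the 50% is only an example, no retention threshold is attached to the endpoint at all. Clarifying the wording would take about a sentence and no new data. Section 23.1 also expects some participants to be re-incarcerated during follow-up, so late surveys are foreseeable, and Section 2.2 does not say whether they count.

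Part of this stands. The literal mismatch is real, and post-release withdrawals are enough to produce it. The weight does not follow. Section 15.1 tells the nurse when to stop calling and when a phone plan may be ended; it does not set up an analysis category, and Section 2.1 does not refer to it. Section 12.1 treats a late survey as the final assessment, merely delayed, which leaves open only how it bears on three-month retention. The obvious repair, scoring criterion (2) as survey completion among released participants, is also more than a clarification. Section 2.2 speaks of study participants, whom Section 4.0 counts as enrolled from consent, and it asks for retention as well as the survey. That repair would change both numerator and denominator of a primary endpoint.

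**Conclusion.** No change is needed. This is loose wording that an analyst resolves sensibly from the plan itself: criterion (2) speaks of completing study activities and of retention, and Section 2.2 supplies the matching primary endpoint. That proportion will be reported whatever the phrase is taken to mean, and loss of nurse contact can be counted from the planned contact log, so a reader can see both figures.

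The possible discrepancy is confined to one setting: the 15.1 meaning is imported into Section 2.1 and the loss rate falls in a band with one edge at 50%. With no completion among the lost, the band is 83–109 of 220 at 80% completion among the others, wider at 70% (63–109), narrower at 90% (98–109), and empty at 100%. The opposite conflict needs the further assumption that a 15.1-lost person counts as retained. All these rates are assumed.

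The stakes are low. This is a single-group pilot sized on nurse caseload (Section 20.2), both success figures are examples, and no formal test, power statement or stopping decision depends on them. The conclusion would differ if the 50% were a binding progression rule; the protocol does not present it as one.
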